3.5. Discontinuation Criteria

Investigational drug dosing in an individual participant will be placed on hold and may be discontinued, following a review of all available clinical data by the medical monitor and discussion with the investigator, if any of the following occurs:

- Any SAE or \geq Grade 3 AE suspected to be related to RDV

Any elevations in alanine aminotransferase (ALT) or aspartate aminotransferase (AST) $> 5 \times$ the upper limit of normal (ULN), confirmed by immediate repeat testing

- Discharge from the hospital/institution
- Intercurrent illness that would, in the judgment of the investigator, affect assessments of clinical status to a significant degree. Following resolution of intercurrent illness, the participant may resume study dosing at the discretion of the investigator

- Unacceptable toxicity, or toxicity that, in the judgment of the investigator, compromises the ability to continue study-specific procedures or is considered to not be in the participant's best interest
- Participant request to discontinue for any reason

All participants will be requested to continue assessments during study hospitalization and any subsequent re-hospitalization to the same institution during Days 1 through 29 and attend the Day 60 phone follow-up (whether hospitalized or as an outpatient).

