6.10. Posttreatment Assessments

Upon discharge from inpatient hospitalization, the following assessments will be required at the Day 29 and Day 60 phone follow-up (see [Appendix 3](#)):

- Assessment of need for RRT
- Record the 8-point ordinal scale (see Section 6.9)
- Review AEs and document concomitant medications

- Mortality
- IMV (yes/no if yes, provide date when mechanical ventilation was started)
- Hospital readmission rate

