6.2.1. Analysis of Secondary Efficacy Endpoints

The key α -controlled secondary endpoint of all-cause mortality through Day 29 will be analyzed in a similar manner to the primary endpoint.

Initiation of IMV through Day 29 and time to recovery through Day 29 will also be analyzed in a similar manner to the primary endpoint except that a competing risk analysis approach will be used with death as the competing risk.

For analysis on time to recovery through Day 29, two sets of analyses will be conducted:

(1) Time to recovery through Day 29, in which the first recovery without further worsening in the ordinal scale score (ie, a score of > 4) by Day 29 will be considered an event; (2) Time to recovery through Day 29, in which the first recovery (regardless of further worsening or not) will be considered an event.

The clinical status assessed by the 8-point ordinal scale at Day 15 and Day 29 will be analyzed using a proportional odds model including treatment as the independent variable. Two models will be explored; one with baseline score as a continuous covariate and one without baseline score as a covariate. The odds ratio and 95% CI will be provided. The percentage of participants in each category will be summarized by treatment group. The assumption of odds proportionality will be assessed using a score test and reported. Clinical status by study day and change from baseline up to Day 29 will also be summarized by treatment group.

For participants without ESKD at baseline, the number of RRT-free days will be calculated between date of first dose and Day 29. The number of RRT-free days will be calculated as the number of full days from Day 1 to Day 29 that the participant was alive and did not receive RRT. The number of RRT-free days will be summarized by treatment group, and compared between treatment groups using Wilcoxon rank sum test.

The proportion of participants with recovery through Day 29 will be summarized by treatment group, and compared between treatment groups using the CMH test stratified by randomization strata. Similar for time to recovery analysis, two sets of analyses will be conducted: (1) The proportion of participants with recovery through Day 29, in which recoveries without further worsening by Day 29 is considered; (2) The proportion of participants with recovery through Day 29, in which recoveries regardless of worsening status by Day 29 is considered.

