The key α -controlled secondary endpoint of all-cause mortality through Day 29 will also be analyzed for each of the subgroups defined in Section 3.4. Other secondary endpoints may also be analyzed for each of the stratification factor subgroups.

For time to event analysis of secondary endpoints, participants with missing outcomes due to premature discontinuation of the study on or prior to Day 29 will be censored at the date of last known status for that endpoint.

Clinical status assessed by the 8-point ordinal scale will be derived by combining the available death, hospital discharge alive and ordinal scale assessment reported by the site, where death supersedes discharge alive and discharge alive supersedes the ordinal scale score reported by the site.

Sites were instructed to report the worst ordinal scale category for each day. Therefore, the ordinal scale result on the day the participant was discharged alive does not necessarily reflect Not hospitalized. The definition of clinical status based on the 8-point ordinal scale is defined as follows:

- If a participant dies on or prior to Day 29, clinical status on the day of death and all subsequent days through Day 29 will be set as 8 (death)
- If a participant is discharged alive on or prior to Day 29, clinical status on the day of discharge alive will be set to 2 (not hospitalized, limitation on activities and/or requiring home oxygen), which is the worst score for a non-hospitalized participant
- If a participant is discharged alive and subsequently re-admitted on or prior to Day 29, and the 8-point ordinal score is not reported on the day of re-admission, the clinical status on the day of the re-admission will be imputed to 7 (hospitalized, on IMV or ECMO), which is the worst score for a hospitalized participant
- For other missing ordinal scores from Day 2 through Day 29, the clinical status will be imputed using the previous day's score (either reported score or imputed score as applicable)

The FAS will be the primary analysis set for the secondary efficacy endpoints.

CCI

[REDACTED]

- [REDACTED]
- [REDACTED]
- [REDACTED]
- [REDACTED]
- [REDACTED]
- [REDACTED]
- [REDACTED]
- [REDACTED]
- [REDACTED]
- [REDACTED]
- [REDACTED]

CCI

CCI

CCI

CCI

CCI

CCI [Redacted]

CCI [Redacted]

[Redacted]

[Redacted]

[Redacted]

[Redacted]

[Redacted]

[Redacted]

[Redacted]

[Redacted]

[Redacted]

[Redacted]

[Redacted]

CCI

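### SAP 6.2.1 scores every re-admission without a same-day ordinal score as category 7 (on IMV or ECMO) without consulting the IMV record, so the ordinal tables can contradict the trial's own ventilation data

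*SAP*

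**What the plan says.** SAP 6.2.1 derives daily clinical status from death, discharge alive and the site's ordinal score, in that order of precedence. Four rules follow.

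- Death: "clinical status on the day of death and all subsequent days through Day 29 will be set as 8 (death".
- Discharge: "clinical status on the day of discharge alive will be set to 2".
- Re-admission by Day 29 with no score that day: "the clinical status on the day of the re-admission will be imputed to 7 (hospitalized, on IMV or ECMO". The stated reason is that this is the score "which is the worst score for a hospitalized participant".
- Any other missing day from Day 2 to Day 29: "the clinical status will be imputed using the previous day's score (either reported score or imputed score as applicable".

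The derived status feeds the Day 15 and Day 29 proportional odds models, the category percentages and the recovery endpoints. Recovery is analysed in two ways. Analysis (1) counts the "first recovery without further worsening in the ordinal scale score", where worsening means a score above 4 by Day 29. Analysis (2) counts the first recovery whatever follows.

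Ventilation is also collected directly. After discharge, Protocol 6.10 lists "IMV (yes/no if yes, provide date when mechanical ventilation was started" for the Day 29 and Day 60 calls. Protocol 3.5 asks for continued assessments during "any subsequent re-hospitalization to the same institution during Days 1 through 29". Protocol 6.4 asks for daily ordinal scores on any re-admission before Day 29, with no mention of institution.

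**The concern.** Category 7 asserts that the participant was on IMV or ECMO. The derivation already combines several data sources, but it leaves out the IMV record, the source that bears most directly on that assertion. The same participant can then have no IMV in the primary and IMV endpoints and be on IMV or ECMO in the ordinal tables.

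Missing scores on re-admission are foreseeable, since Protocol 3.5 limits continued assessment to the same institution. A re-admission that needed no oxygen is category 3 or 4 and would not undo a recovery in analysis (1). An imputed 7 does. The sensitivity analyses in SAP 6.1.4 concern the primary endpoint only, and the visible text plans none for this rule.

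**Working it through.** **Plan figure.** The documents give no re-admission rate, no rate of missing scores and no expected ordinal odds ratio. The only power statement (about 85%) concerns the primary endpoint, so there is no figure to reproduce on this point.

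**Step 1: the rules applied day by day.** Take a participant discharged on Day 8 and re-admitted on Day 14 with no score that day.

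| Later data | Derived status | Analysis (1) | Analysis (2) |
|---|---|---|---|
| Phone score 2 on Day 29 | 7 on Days 14–28, then 2 | Day 8 recovery lost, or delayed to Day 29 | Day 8 |
| Phone call on Day 31 | 7 on Days 14–29 | lost | Day 8 |
| Second discharge on Day 17 | 7 on Days 14–16, then 2 | Day 8 recovery lost, or delayed to Day 17 | Day 8 |
| Score 4 reported on Day 15 | 7 on Day 14 only, then 4 | Day 8 recovery lost | Day 8 |
| For comparison: score 4 reported on Day 14 | 4 from Day 14 | Day 8 kept | Day 8 |

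Lost or delayed depends on whether analysis (1) means the first recovery or the first sustained one.

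The second row is possible because the phone visits have a window of +5 days (Protocol Appendix 3), while SAP 3.8.2 maps ordinal scores to the exact study day. A call on Days 30–34 does not fill Day 29.

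A true re-admission score of 5 or 6 would have undone the recovery in analysis (1) anyway. The rule is wrong there only when the true status was 4 or lower.

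**Step 2: effect on the ordinal odds ratio.** All inputs are assumptions.
- Placebo Day 29 distribution, categories 1 to 8: 30/25/3/4/6/3/5/24%.
- Allocation 2:1. RDV distribution from odds(Y ≤ k | RDV) = 1.50 × odds(Y ≤ k | placebo), so values above 1 favour RDV.
- A share q of each arm's category 1–2 participants is re-admitted and unscored. They are moved to category c, and the unadjusted proportional odds model is fitted to the expected proportions.

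The cost of the rule is the c = 7 column against the column for the true hospitalised category.

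| q placebo / q RDV | c = 4 | c = 5 | c = 6 | c = 7 |
|---|---|---|---|---|
| 2% / 2% | 1.49 | 1.49 | 1.49 | 1.49 |
| 5% / 5% | 1.48 | 1.48 | 1.47 | 1.47 |
| 10% / 10% | 1.47 | 1.46 | 1.45 | 1.44 |
| 10% / 5% | 1.57 | 1.58 | 1.59 | 1.59 |
| 5% / 10% | 1.38 | 1.36 | 1.35 | 1.33 |

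With equal shares, choosing 7 over the true category costs at most 1.465 − 1.441 = 0.024. With unequal shares it adds 1.593 − 1.572 = 0.021 in one direction or removes 1.380 − 1.330 = 0.050 in the other.

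With an underlying odds ratio of 1.00, equal shares leave it at 1.00. Shares of 10%/5% give 1.08 with category 7 and 1.06 with category 4. Shares of 5%/10% give 0.92 and 0.94 (0.923 and 0.945 before rounding).

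If the participant was in fact home again with the second discharge not captured, the comparison is with 1.50 itself. The range for category 7 is then 1.33 to 1.59.

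**Step 3: power.** Planned enrolment was 1116, and enrolment stopped before 50% (558), so N = 557 (186 placebo, 371 RDV) is an upper limit. With a rank test, 40,000 simulated trials and 8% re-admitted and unscored in both arms, power is 66.4% if all are truly category 5 and 64.4% with category 7. The rule costs about 2 points.

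**The case against.** The rule is prespecified and openly worst-case, and it parallels the discharge rule, which assigns the worst non-hospitalised score. Carry-forward already stops at a reported score, second discharge or death. Protocol 6.4 asks for daily scores on re-admission, and the Day 29 call records a score of its own, so the missing-score case may be uncommon. The affected endpoints are outside the alpha-controlled hierarchy (SAP 3.5). The IMV data are also incomplete for this purpose: the post-discharge list in Protocol 6.10 has no ECMO item and no IMV stop date, and the re-admission list in Protocol 6.4 omits IMV. Redacted text in the SAP may contain related analyses.

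All of this stands, and it limits the weight of the point. It does not explain assigning category 7 when the IMV record rules out ventilation.

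A reader might infer that the rule pulls the ordinal effect toward the null and costs several points of power. The documents do not support that. The direction depends on how imputed 7s fall between arms, and more of them on placebo moves the odds ratio away from 1. Comparing category 7 with categories 1–2 gives a larger loss (71.4% to 64.4% at 8%, in the setting of Step 3), but most of it comes from the re-admission itself, not from the choice of 7.

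**Conclusion.** The point holds as a should-fix on secondary endpoints. The rule can put the ordinal tables in conflict with the trial's IMV data, and in recovery analysis (1) it can remove or delay a recovery when the true re-admission status was 4 or lower.

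A reader might also infer that recoveries are cancelled generally, or that the primary result is affected. Analysis (2) ignores later worsening. Nothing in the visible text feeds the imputed 7 into the primary, mortality or IMV-initiation endpoints, though the SAP does not expressly exclude this.

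The effect on the ordinal odds ratio is probably small: within about 0.02 of the value under the true hospitalised category when arms are balanced, and up to about 0.05 either way in the unbalanced cases tried. These sizes rest on an assumed category distribution, an underlying odds ratio of 1.50 and re-admitted, unscored shares of 2–10%. The number actually affected is unknown.

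**What to change.** In SAP 6.2.1:

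1. Impute 7 on re-admission only if IMV or ECMO is recorded on or after the re-admission date, or if that status is unknown. If the record shows neither, impute 6, the worst hospitalised category consistent with the data. Keep the existing carry-forward and stopping rules.
2. State what counts as ruling out ECMO after discharge. Protocol 6.10 asks only about IMV, so if a missing ECMO item counted as unknown, category 6 might rarely be used. A recorded no for IMV, with no ECMO recorded anywhere, is a workable definition.
3. Report the number of imputed re-admission scores by arm and by category.
4. Repeat the Day 15 and Day 29 status analyses and recovery analysis (1) under the current all-7 rule and with category 4. The category 4 run is the one that informs recovery, because an imputed 6 still exceeds 4 and undoes a recovery just as 7 does.
5. State that the imputed status is not used for the primary, mortality or IMV endpoints.

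The cost is a few lines of derivation, one small table and two repeat runs on data already collected. The main analysis no longer uses the absolute worst hospitalised score when the data rule it out. SAP Section 1 provides for finalisation before unblinding; a later change would have to be documented in the CSR.

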6.2. Secondary Efficacy Endpoints

The key α -controlled secondary endpoint is all-cause mortality through Day 29.

Other secondary endpoints include:

- Initiation of IMV through Day 29
- Time to recovery through Day 29
- Clinical status assessed by the 8-point ordinal scale at Day 15 and Day 29
- RRT-free days (among those without ESKD at baseline) through Day 29
- Proportion of participants with recovery through Day 29

Recovery is defined as achieving category 1, 2, or 3 on the 8-point ordinal scale score, for participants with a baseline score ≥ 4 .

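### Carry-forward of the ordinal score has no stop at study discontinuation, so participants who leave while inpatient enter the Day 15 and Day 29 models at a fixed in-hospital category, and the SAP does not say whether a carried score counts as last known status for time to recovery

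*SAP*

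**What the plan says.** SAP 6.2.1 derives daily clinical status in a fixed order. Death sets 8 from the day of death through Day 29. Discharge alive sets 2 on the day of discharge. Readmission without a reported score sets 7 on that day. A general rule follows: "For other missing ordinal scores from Day 2 through Day 29, the clinical status will be imputed using the previous". The sentence goes on to name the score of the day before, and that value may be "either reported score or imputed score as applicable". No limit on length is given, and there is no exception for leaving the study.

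Three uses of the score matter here.

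- **Day 15 and Day 29 status.** "The clinical status assessed by the 8-point ordinal scale at Day 15 and Day 29 will be analyzed using a proportional odds model" with treatment as the independent variable, with and without baseline score.
- **Recovery.** SAP 6.2: "Recovery is defined as achieving category 1, 2, or 3 on the 8-point ordinal scale score, for participants with a baseline score" of at least 4. The proportion recovered is compared by a CMH test, once counting any recovery and once where only "recoveries without further worsening by Day 29 is considered".
- **Time to recovery.** One rule covers those who leave early, and it opens by naming its scope: "For time to event analysis of secondary endpoints, participants with missing outcomes due to premature discontinuation of the study on or prior to Day 29". Under that rule their follow-up "will be censored at the date of last known status for that endpoint".

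SAP 3.6.1 declares the ordinal scale an exception to its general rule against imputation. Protocol 6.11 allows withdrawal from the study. Protocol 6.4 and 6.10 have the scale recorded daily until discharge and then by phone at Day 29 and Day 60.

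**The concern.** Because carried scores can themselves be carried, one last score can run from the day a participant leaves to Day 29. For a participant who leaves from a hospital bed, that turns an unknown outcome into an observed one. The odds ratio for clinical status can then be biased, mainly when inpatient withdrawal differs between arms, and the interval takes no account of the uncertainty.

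A second issue concerns reproducibility. Time to recovery rests on the same ordinal score. If the derived score is used, no score after Day 1 is missing, so the condition that triggers censoring may never be met. If only reported scores are used, it is met. Two programmers could give the same participant different censoring days.

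The readable text offers no sensitivity analysis for either matter. Those in SAP 6.1.4 concern the primary endpoint only.

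**Working it through.** There is no figure in the plan to reproduce; the point rests on the rules. The check has three steps.

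**1. Apply the SAP 6.2.1 rules to typical exits**

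| Exit pattern | Day 15 | Day 29 | Status known? |
|---|---|---|---|
| Leaves Day 6, inpatient on oxygen (5) | 5 | 5 | No |
| Leaves Day 6 on IMV (7) | 7 | 7 | No |
| Leaves Day 6 in category 3 | 3 | 3 | No, but first recovery was observed |
| Discharged, readmitted without a score, then lost | 7 | 7 | No |
| Leaves Day 6 on oxygen, death known on Day 20 | 5 | 8 | Day 29 yes, Day 15 no |
| Discharged Day 6, then lost | 2 | 2 | Not an in-hospital status |
| Discharged Day 6, Day 29 call gives 1 | 2 | 1 | Day 29 yes |

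An in-hospital status is fixed through Day 29 only in the first four rows. No first recovery is created by carry-forward in any row.

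**2. Time to recovery**

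Take the first row. Censoring on observed scores gives Day 6. If carried scores count as known, it gives Day 29, which is 29 − 6 = 23 further days at risk without recovery. The SAP text does not choose.

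**3. Size for Day 29 status**

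All inputs are assumptions, because the documents give neither withdrawal rates nor a status distribution. Placebo at Day 29: 63% in categories 1–2, 11% in categories 3–7, 26% dead. The true odds ratio for worse status is 0.70, allocation is 2:1, and every leaver's last score is 5. With w the proportion leaving, the analysed distribution in an arm is (1 − w) × true distribution, plus w at category 5.

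True remdesivir probabilities:

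- Above category 2: placebo 0.37, odds 0.37/0.63 = 0.587; × 0.70 = 0.411; probability 0.411/1.411 = 0.291.
- Death: placebo 0.26, odds 0.26/0.74 = 0.351; × 0.70 = 0.246; probability 0.246/1.246 = 0.197.

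At the lower cut a leaver counts as worse, so the probability is w + (1 − w)p. At the death cut it is (1 − w)p. For 10% in both arms:

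- Lower cut: 0.10 + 0.90 × 0.291 = 0.362 versus 0.10 + 0.90 × 0.37 = 0.433; odds ratio 0.568/0.764 = 0.74.
- Death cut: 0.178 versus 0.234; odds ratio 0.216/0.305 = 0.71.

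The fitted proportional odds estimate pools the cuts. I obtained it by large-sample maximum likelihood. Different splits of the 11% over categories 3–7 moved it by no more than about 0.01.

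| Leaving, RDV / placebo | Odds ratio, cut above 2 | Odds ratio, death cut | Fitted, true 0.70 | Fitted, true 1.00 |
|---|---|---|---|---|
| 2% / 2% | – | – | 0.705 | 1.00 |
| 5% / 5% | 0.72 | 0.70 | 0.71 | 1.00 |
| 10% / 10% | 0.74 | 0.71 | 0.72 | 1.00 |
| 3% / 8% | 0.63 | 0.75 | 0.66–0.67 | 0.94–0.95 |
| 8% / 3% | 0.84 | 0.66 | 0.76–0.77 | 1.06 |

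The two cut columns are for a true odds ratio of 0.70. For scale, SAP 2.4 says enrollment stopped before 50% of plan, so there are fewer than 0.5 × 1116 = 558 participants. At 557, with an assumed spread of the categories, the standard error of the log odds ratio is about 0.16. Equal withdrawal of 5% or 10% shifts the log odds ratio by ln(0.71/0.70) = 0.014 or ln(0.72/0.70) = 0.028, which is 0.1 to 0.2 standard errors. The 8% / 3% case shifts it by ln(0.76/0.70) = 0.082, about 0.5.

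**The case against.** The case for leaving the rule alone is reasonable. It is prespecified, treats both arms alike, and is a declared exception to the no-imputation principle. The primary endpoint and the mortality endpoint do not use it. Carry-forward also does necessary work: daily scoring ends at discharge, so it is what gives a discharged participant a Day 15 status. The protocol works against loss: stopping drug is not leaving the study, and sites are to make every attempt to retain participants (Protocol 6.11). The effect on precision is small too. Against dropping 5% or 10% of participants, sample size alone makes the standard error smaller by factors of √0.95 = 0.975 or √0.90 = 0.949. All of this stands, and it limits the point to inpatient leavers and to a modest size.

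Three stronger readings might be inferred, and the documents do not support them.

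- **That carry-forward contradicts the censoring rule.** The censoring sentence is confined to time-to-event analyses, while Day 15 and Day 29 status goes into a proportional odds model. In ordinary usage a carried score is not a known status either. What is left is an omission, for time to recovery only.
- **That everyone who leaves is fixed at an in-hospital status.** Discharge, known death and the Day 29 call cover most other exits.
- **That both recovery proportions are distorted.** A participant who leaves unrecovered counts as not recovered in any proportion of the Full Analysis Set, with or without carry-forward. A recovery reached before leaving was observed. Only the version without later worsening assumes something unseen, namely that a participant who left in category 3 did not worsen. Censoring cannot address that in a CMH test.

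**Conclusion.** The point holds in a limited form. As written, a participant who leaves while inpatient, or is readmitted and then lost, is analysed at Day 15 and Day 29 in a category nobody observed, and the readable text has no check on it. The time-to-recovery censoring day is also left open.

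Equal withdrawal only pulls a true effect slightly toward 1 and gives no bias under no effect. Unequal withdrawal is what matters: an arm difference of 3% against 8% moves 0.70 to about 0.67 or 0.76, and can move 1.00 to about 0.95 or 1.06. These figures depend on assumed withdrawal rates and on every leaver's last score being 5. With 2% leaving per arm the change is 0.005. The endpoints are secondary and outside alpha control (SAP 3.5), so severity is minor.

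**What to change.** Amend SAP 6.2.1 in three places.

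1. Limit carry-forward to gaps while the participant is still in the study. Keep it for the days between discharge and the Day 29 call.
2. For Day 15 and Day 29 status, treat scores after the study discontinuation date as missing, with known deaths still set to 8. Use multiple imputation from arm, baseline score and last observed score. If too few leave for a stable model, use an analysis that excludes them. Report the present rule alongside as a sensitivity analysis, with the number of leavers by arm.
3. State that time-to-recovery censoring uses observed scores only.

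The cost is a few sentences, a little extra programming and a slightly wider confidence interval.
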